*Data analysis:* The data will be analysed by intention to treat. IPV incidence will be compared between arms in the study. The primary analysis will be carried out by fitting a Poisson regression model, which will include terms for age of participant, cluster, baseline prevalence of IPV (for males or females) and treatment (arm). Other quantitative variables will be analysed with change from baseline compared between arms using GLMMs.

*Qualitative:* The data will be analysed using thematic network analysis. Coding will take place focused on the key questions to be answered in the study with separate analysis for women and men.

*Integrated process evaluation:* An integrated process evaluation will be conducted to explore how facilitators delivering the intervention to so. Ethnographic and qualitative methods will be used.

*Costing analysis:* The costing data will be analysed using a provider and client perspective using incremental cost-effectiveness will be calculated using the primary outcome, with costs set at 2017 rates.

*Project management:* The intervention is funded through the What Works to Prevent Violence Global Programme. Access to communities, recruitment of participants for the research and intervention delivery is the responsibility of Project Empower. The research is a project of HEARD at the University of KwaZulu Natal, with collaborators from the Medical Research Council. The study will be conducted over 3 years with recruitment commencing soon after ethics approval. The research will be conducted over 24 months and there will be 6 months for data analysis and writing up the findings and dissemination, and 6 months for intervention scale up if the findings are positive.

**OUTCOME:** This research will generate knowledge on the efficacy of an intervention to prevent IPV among an extremely vulnerable and disadvantaged sector of South African society. The study will extend knowledge globally of interventions to prevention of gender-based violence.

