### 7.7.1 Sample size calculation:

In the pilot study conducted in 2012-13 the past year prevalence of physical and/or sexual IPV perpetration and victimisation was 45% among men and 41% among women. These levels of violence are exceptionally high by South African standards, so we have modelled the sample size on a range of possible baseline rates (see the table). The sample size assumes 14 will be followed up per cluster (of the 20), but figures are robust to a follow up of only 12 in each cluster. Assuming a coefficient of variation  $k=0.2$  and modelling 80% power. The table shows that with 14 male (and 14 female) participants per cluster and 16 clusters we will have power to detect a range of possible incidence and impact scenarios and to analyse men and women separately (see table). Our power will be further enhanced by having multiple assessments and an additional two clusters.

IPV incidence (12 months)			# of clusters required by arm
11	12	power	
36	29	80	16
45	36	80	15
41	33	80	16
24	19	80	14
18	14	80	13
30	24	80	15

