## 7.8 Study's main outcomes

### *Primary outcome:*

The past year incidence of IPV (perpetration of physical and/or sexual IPV for men and victimisation for women), including change in controlling behaviour.

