## 10.2 Data analysis

The main analysis will be by intention to treat but a *per protocol* analysis will also be conducted as a secondary analysis.

Any participant who responds affirmatively to any one of the five questions on physical intimate partner violence or three questions on sexual intimate partner violence in the past 12 months at the 24 month data collection points will be deemed to be an incident case of IPV victimisation (if female) or perpetration (if male).

IPV incidence will be compared between the study arms. The person years of exposure will be estimated as the time from the baseline to the first report of IPV (if this is reported during the study) or to the last interview, if they remain IPV free at the end of the study. Separate analyses will be done for males and females. The primary analysis will be carried out by fitting a Poisson regression model, which will terms for age of participant, cluster, baseline prevalence of IPV (for males or females) and treatment (arm). For each secondary outcome a Generalised Linear Mixed Models (GLMMs) will be fitted with similar terms as in the Poisson regression model for the main outcome. These will be fitted for time from baseline to interview (12 months and 24 months). Secondary analysis of the main outcome will also be done using a multi-level model for change. Generalised Linear Mixed model for binary outcome will be used.

Analyses for secondary outcomes will follow the same approach for variables where incidence can be measured. For outcomes using scales, the difference in the score/scale between baseline and 24 months measure will be assessed. For each of the scales a linear mixed model will be fitted with fixed terms for treatment arm. Separate models will be fitted for males and females. The scores will be directly calculated from the component items, while the scales will combine the items using weights determined by carrying out a principal component analysis on the items at baseline (separately for males and females), and using the loadings for the first principal component as the weight for each item. The baseline weights (separate for males and females) will be used to construct the scale at each time point. These analyses will firstly be carried out in the ITT population and then repeated for the per protocol population.

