### **Costing Analysis**

In order to estimate the total cost of the SS/CF intervention, the cost of both the retrospective and prospective components of the study outlined above will be analysed. This includes the direct and indirect costs from the perspective of the service providers and the participants. Research related costs will be excluded from the analysis.

In order to conduct the cost-effectiveness analysis, incremental cost-effectiveness will be calculated using primary and selected secondary outcomes of the SS/CF intervention. The primary outcome in the RCT is incidence in the past year of intimate partner violence (perpetration of physical and/or sexual IPV for men and victimisation for women), including change in controlling behaviour. Key secondary outcomes include gender attitudes; depression; problem drinking; sexual behaviour and mean earnings in last month. The time and motion data will be used together with the salary costs paid to the facilitators to identify the proportion of labour resources used and costs relating to core activities in the intervention, administrative activities and non-core activities.

Costs and outcomes are compared against the control group, who receive no intervention in the initial timeframe as set out in the RCT design. Cost-effectiveness will be assessed as the intervention cost per participant divided by the effectiveness of the intervention.

The cost data collected at different time points in the study will also be used to estimate the incremental efficiency gains as the facilitators become familiar with the intervention and the material they present. These data will be used to better understand resource use as the intervention rolls out and has implications for estimating the costs of scale-up.

We will use a standard annual discount rate of 3%, and run sensitivity analyses will be conducted using local discount rates, to check the robustness of results to these changes. Total costs will be reported in USD2017, using official exchange rates.

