2.5. Outcomes

2.5.1. Primary outcomes

- Four primary outcomes are linked to IPV:
 - Any past year physical IPV perpetration (men), and experience (women). This is assessed using a modified WHO VAW scale that has been adapted and widely used in South Africa. Five questions are asked about physical IPV perpetration (men) and experience (women) in the past 12 months. Past year physical IPV is coded as positive (1) for anyone responding positively to one or more items on the scale;
 - Any past year sexual IPV perpetration (men), and experience (women) uses the same approach as for physical IPV. Three sexual IPV questions are asked about experiences in the past 12 months. Past year sexual IPV is coded as positive (1) for anyone responding positively to one or more items on the scale;
 - To assess severe past year sexual and/or physical IPV perpetration (men) and experience (women), physical and sexual IPV scales are combined to be a total of eight items. Past year severe sexual and/or physical IPV is assessed as positive if a person responds to two (or more) items once, or one item as few (or more), essentially creating a more than once categorization.
 - Controlling behaviours are assessed using a modified Sexual Relationship Power (SRP) scale [43] with 8 items. Higher scores refer to more controlling behaviours;
- One primary outcome reflects the objective of the Creating Futures component of the intervention, around strengthening livelihoods:
 - Past month earnings are used to assess overall income and livelihoods. A single item question asks, “Considering all the money you earned from jobs or selling things (excluding grants), how much did you earn last month?” Responses are in South African Rands (ZAR) and a continuous scale.

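### The SAP lists no outcome equal to the protocol's primary IPV outcome, any past-year physical and/or sexual IPV, and gives no reason for leaving it out

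*SAP*

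**What the plan says.** **Protocol.** Section 7.8 gives the primary outcome as "The past year incidence of IPV (perpetration of physical and/or sexual IPV for men and victimisation for women), including change in controlling behaviour". Section 10.2 defines a case: "Any participant who responds affirmatively to any one of the five questions on physical intimate partner violence or three questions on sexual intimate partner violence", over the past 12 months at the 24-month data collection. Section 7.7.1 starts the sample size from the pilot figure for the same composite: "the past year prevalence of physical and/or sexual IPV perpetration and victimisation was 45% among men and 41% among women". It then spreads the assumption: "so we have modelled the sample size on a range of possible baseline rates". The Costing Analysis section restates the outcome: "The primary outcome in the RCT is incidence in the past year of intimate partner violence (perpetration of physical and/or sexual IPV for men". It describes the calculation as "Cost-effectiveness will be assessed as the intervention cost per participant divided by the effectiveness of the intervention". The executive summary says the same more briefly: "incremental cost-effectiveness will be calculated using the primary outcome, with costs set at 2017 rates".

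**SAP.** Section 2.5.1 lists five primary outcomes: any physical IPV (5 items), any sexual IPV (3 items), severe physical and/or sexual IPV (the same 8 items), controlling behaviours, and past-month earnings. For severe IPV the rule is "Past year severe sexual and/or physical IPV is assessed as positive if a person responds to two (or more) items once", or a single item reported as few times or more. Table 2 accordingly groups once with never. The union with a one-act threshold is absent from Tables 1 and 2, from the secondary outcomes and from the additional analyses in 3.5.3. Section 3.3 does use past-year physical and/or sexual IPV, but only at baseline, to choose covariates.

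**Earnings.** The protocol lists past-month earnings as a secondary outcome and places livelihoods under the secondary objective (7.1). The SAP makes earnings primary. It ties this to the aim of Creating Futures but does not say that the status has changed.

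**The concern.** A reader going from protocol to SAP expects to find the outcome the trial was designed on and finds only pieces of it. A person who reports one act once still counts under physical or sexual IPV. What is missing is the treatment effect on whether a participant had any IPV at all.

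Two things depend on that effect. One is the answer to the protocol's main question in the form the protocol asked it. The other is the cost-effectiveness ratio, whose denominator is effectiveness on an outcome that the costing section defines as this union.

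There is also a documentation gap. The SAP explains neither the omission of the union nor the change in the status of earnings.

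**Working it through.** **1. Do any of the SAP outcomes equal the union?** There are eight items with four responses each (never, once, few, many), so 4^8 = 65,536 response patterns. All but the all-never pattern are protocol cases: 65,535. Of these:

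- severe IPV misses 8 (exactly one item, answered once);
- physical IPV misses 4^3 − 1 = 63 (sexual items only);
- sexual IPV misses 4^5 − 1 = 1,023 (physical items only).

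Each is a strict subset and none is the union. These are counts of patterns, not shares of participants, which the documents do not give.

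**2. Can the union effect be recovered from the listed effects?** Union = P + S − B, where B is the share reporting both types. No listed outcome estimates B. Component prevalences are not given, so as an assumption for men take P = 35%, S = 20%, B = 10%; the union is then 35 + 20 − 10 = 45%, matching the pilot figure. Let each component fall by 20%, to P = 28% and S = 16%.

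| B after | Union after | Relative fall in union |
|---|---|---|
| 10% | 34% | 11/45 = 24% |
| 8% | 36% | 9/45 = 20% |
| 5% | 39% | 6/45 = 13% |

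From P and S alone, the union could lie anywhere from 28% (B = 16%) to 44% (B = 0), a fall of 38% to 2%. For women, with assumed P = 30%, S = 20%, B = 9% (union 41%), the same steps give a union of 24% to 40%, a fall of 41% to 2%.

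**3. What severe IPV adds.** Anyone reporting both types has at least two positive items and so is severe-positive. The union therefore cannot be below the severe prevalence, and it exceeds it by exactly the share reporting one item once. If, as an assumption, severe prevalence in men after intervention were 30%, the largest possible fall in the union would be (45 − 30)/45 = 33%, not 38%. The limits tighten, but the effect is still not determined.

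**4. Power.** Clusters per arm = 1 + (1.96 + 0.84)² × [(p0(1−p0) + p1(1−p1))/m + k²(p0² + p1²)]/(p0 − p1)², with m = 14 and k = 0.2 (protocol 7.7.1), two-sided 5% (SAP 3.2), 80% power and p1 = 0.8 p0. This does not reproduce the protocol's table (46.9 at 45% against 36%, where the table gives 15). That is a separate matter, and only ratios are used here.

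| | Union | Physical, assumed rate | Ratio |
|---|---|---|---|
| Men | 45%: 46.9 | 35%: 62.9 | 1.34 |
| Women | 41%: 52.4 | 30%: 74.9 | 1.43 |

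The more common component is at least half the union. At that extreme (two equal components, no overlap) the ratios are 102.9/46.9 = 2.19 for men and 113.8/52.4 = 2.17 for women. If one component makes up the whole union, the ratio is 1.0. All these component rates (20.5% to 45%) lie within the 18% to 45% that the protocol's table covers.

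**5. Cost in false positives.** With five primary tests per sex, if independent, the chance of at least one false positive is 1 − 0.95^5 = 22.6%. With six it is 1 − 0.95^6 = 26.5%. The union overlaps strongly with tests already listed, so the real rise is smaller.

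**The case against.** **The governing protocol may be elsewhere.** The SAP cites a protocol published in 2017, which was not supplied and may have changed the outcomes. This stands. The omission is certain on the supplied text; whether it departs from the version in force is not. A reader might infer undisclosed outcome switching. The documents do not support that: they show an unexplained difference and nothing about motive.

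**The severe composite nearly does the job.** It uses the same eight items and differs only for people with one item reported once. That narrows the range in step 2, so the 2% to 41% limits should not be read as what the SAP leaves open. But the size of the one-act group is not given, and its response to treatment is not estimated.

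**Power.** A reader might infer that splitting the outcome doubles the required clusters. That needs two equal components with no overlap; at the assumed rates the ratio is 1.34 to 1.43, and it can be 1.0.

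**Cost-effectiveness can use other outcomes.** The costing section also allows selected secondary outcomes, the SAP does not cover costing, and the union can be derived from the data. All true. The outcome that the costing section calls primary would still have no planned estimate.

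**The proposed outcome is not exactly the protocol's.** Section 7.8 speaks of incidence without a time point and includes controlling behaviour, and section 10.2 also counts person-time to first report. The SAP keeps controlling behaviours as primary. The point here is the case definition at 24 months; the person-time Poisson analysis is a separate matter.

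**Conclusion.** The point holds on the supplied documents. The protocol's primary IPV outcome appears nowhere among the SAP's outcomes, and the SAP gives no reason. Followed as written, the trial would report no effect estimate for the IPV outcome from which its sample size starts and which its costing section names as primary.

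The listed outcomes bound that effect but do not determine it. Under the assumed rates for men, equal 20% falls in both components are compatible with falls in the union of 13% to 24% at the three overlaps tried; severe IPV would limit the wider extremes. Any loss of power is unknown and may be nil. The conclusion on the omission rests on reading alone; the percentages rest on assumed component rates. Whether the change was formally made, and so what status the union should have, depends on the unseen 2017 protocol.

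**What to change.** Add to SAP 2.5.1 and to Tables 1 and 2 the outcome any past-year physical and/or sexual IPV at 24 months (one or more of 8 items). Analyse it separately for women and men, as protocol 10.2 requires, with the GEE of SAP 3.5.1 and the same covariates as the other binary IPV outcomes. SAP 3.3 and 3.5.2 list different covariate sets, so name the one that applies.

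List the union as primary, as in the supplied protocol. If the published 2017 protocol formally changed the primary outcome, cite it and report the union as a named secondary or additional outcome. Keep every outcome the SAP already lists. Add a short statement giving the date and reason for each departure from the protocol's outcome list: the union left out, and earnings moved from secondary to primary.

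The cost is some SAP wording, one variable derived from items already collected, and one more model per sex. As a primary outcome it takes the unadjusted 5% tests from five to six per sex, assuming the SAP also intends separate analyses by sex, which it does not state outright.

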2.5.2. Secondary outcomes

Five groups of secondary outcomes are identified focused on pathways to change through which the intervention is hypothesized to operate.

- The first pathway reflects gender attitudes and norms in the group:
 - Gender attitudes are assessed using a modified Gender Equitable Men’s Scale (GEMS) [44] adapted and widely used in South Africa [18]. The scale comprises of 20 questions, with larger scores indicating less gender equitable attitudes. It is hypothesized the mean will decrease.
- Three sets of questions assess mental health and wellbeing:
 - Past week depressive symptomatology is assessed by the Centre for Epidemiologic Studies Depression (CESD) scale, with the full twenty items [45]. Higher scores indicate greater depressive symptomatology. A mean score for each participant will be calculated. It is hypothesized the mean score will reduce.
 - Past four-week suicidal ideation is assessed using a single item question and a binary yes/no response. It is hypothesised that the percentage of participants reporting yes to this will decrease.

- Life circumstances are assessed using four items derived from the Satisfaction with Life Scale [46]. Higher scores indicate greater life satisfaction. It is hypothesized the mean score will increase.
- Two questions assess the impact of the intervention on alcohol use amongst participants as secondary outcomes:
 - Problem drinking in the past year is assessed using the ten item Alcohol Use Disorders Identification Test (AUDIT) scale. It is hypothesized that there will be a reduction in the mean difference of problem alcohol use.
 - A single item assesses quarrelling in the past year about alcohol consumption with a sexual partner, assessed with a binary yes/no response. The intervention assumes the percentage reporting quarrelling about alcohol use will decrease.
- Two items assess sexual risk behaviour.
 - A single item assesses who the participant last had sex with. Response options are: “main partner, kwapheni (casual) partner, once-off sex partner, ex-partner.” Responses will be coded into a binary of main partner (1) or other sex partner (0). It is hypothesized that the percentage of participants reporting last sex with a main partner will increase.
 - Transactional sex with a kwapheni or once-off sexual partner in the past year will be assessed using a five-item scale used widely in South Africa [48]. A positive response to at least one of these items is classified as responding positively to transactional sex in the past 12 months. It is hypothesized this will reduce.
- Livelihoods are assessed using four scales assessing material outcomes and psychological outcomes of limited income and work opportunities.
 - Shame about lack of work is assessed using four items drawn from the IMAGES study [49]. Higher scores indicate greater levels of shame about lack of work and income. A mean score will be calculated for each participant and it is hypothesized the score will reduce.
 - Stress related to lack of work and income is assessed on a four-item scale drawn from the IMAGES study [49]. Higher scores indicate higher levels of stress about lack of work. A mean score will be calculated for each participant and it is hypothesized the score will reduce.
 - Ability to mobilize cash in an emergency will be assessed with a single item. For analysis a binary will be created through collapsing very difficult and somewhat difficult to indicate challenges (and coded 0), while fairly easy and easy will be coded as no challenge (1). It is hypothesized the percentage of respondents reporting it is fairly easy or easy will increase.
 - Stealing in the past four weeks because of hunger or lack of money will be assessed with a single item. Responses are: Never, once, two or three times, more often. Once, two or three times and more often will be collapsed together for analysis as indicating stealing because of hunger or lack of money. It is hypothesized this will decrease.

This has been summarized in **Table 1**.

Table 1: Primary and secondary trial outcomes

Item	Response categories	Number of items
Primary outcomes		
Physical IPV at 24 months	In the last 12 months how, many times did you push or shove your current or previous girlfriend or wife?	Never, once, few, many 5
Sexual IPV at 24 months	In the last 12 months, how many times have you ever forced your current or previous girlfriend or wife to do something sexual that she did not want to do?	Never, once, few, many 3
Severe IPV at 24 months	Same as above	Never, once, few, many 8
Controlling behaviours at 24 months	I want to know where my partner is all the time.	Strongly disagree, disagree, agree, strongly agree 8
Earnings in the past month at 24 months	Considering all the money you earned from jobs or selling things, how much did you earn in the last 4 weeks (not including grants)?	Continuous variable 1
Secondary outcomes		
Gender attitudes at 24 months	I think that a woman needs her husband's permission to do paid work	Strongly disagree, disagree, agree, strongly agree 20
Depressive symptomology (CESD) at 24 months	During the past week I thought my life had been a failure	Rarely/none of the time, some/little of the time, moderate amount of time, most/all of the time 20
Suicidal ideation at 24 months	In the past four weeks, has the thought of ending your life been in your mind?	Yes, no 1
Life circumstances at 24 months	The conditions of my life are excellent	Strongly disagree, disagree, neither agree or disagree, agree, strongly agree 4
Problem alcohol use (AUDIT) at 24 months	How often in the past year have you had a feeling of guilt or remorse after drinking?	Several items 10
Quarreling about alcohol at 24 months	In the past 12 months have you quarreled with any of your female sexual partners about your drinking?	Yes, no 1
Last sexual partner at 24 months	The last time you had sex was it with a main partner, another partner (khwapeni) or one-off partner or expartner?	Main partner, casual partner, once-off, expartner 1
Transactional sex at 24 months	In the past 12 months, please think about any woman you had sex with just once or any casual partner or khwapeni. Do you think any of them may have become involved	Yes, no 5

	with you because they expected you to give or you gave cash or money to be looked after?		
Work shame at 24 months	I am ashamed to see my girlfriend because I don't have money	Strongly disagree, disagree, agree, strongly agree	4
Work stress at 24 months	I am frequently stressed or depressed because of not having enough work	Strongly disagree, disagree, agree, strongly agree	4
Stealing because of hunger at 24 months	How often in the past 4 weeks have you taken something that was not yours because you did not have enough food or money?	Never, once, two or three times, more	1
Mobilization at cash in emergencies at 24 months	If you had an emergency at home and needed R200, how easy would you say it would be to find the money?	Very difficult, somewhat difficult, fairly easy, easy	1

3. General analysis principles

